## 6.0 CRITERIA FOR SUBJECT ELIGIBILITY

### 6.1 Subject Inclusion Criteria

- History of histologically confirmed colorectal adenocarcinoma metastatic to the liver with no clinical or radiographic evidence of extrahepatic disease. Confirmation of diagnosis must be performed at MSKCC.
- Completely resected hepatic metastases without current evidence of other metastatic disease.
- Lab values  $\leq$  14 days prior to treatment start:
  - WBC  $\geq$  3.0 K/uL
  - ANC  $>$  1.5 K/uL
  - Platelets  $\geq$  100,000/uL
  - Creatinine  $<$  1.5 mg/dL
  - HGB  $\geq$  9 gm/dL
- Renal function ( $\leq$  14 days prior to treatment start).
  - Creatinine  $\leq$  1.5 mg/dL or creatinine clearance  $\geq$  50 mL/min calculated by the Cockcroft-Gault method as follows:
    - Male creatinine clearance =  $(140 - \text{age in years}) \times (\text{weight in Kg}) / (\text{serum Cr in mg/dL} \times 72)$
    - Female creatinine clearance =  $(140 - \text{age in years}) \times (\text{weight in Kg}) \times 0.85 / (\text{serum Cr in mg/dL} \times 72)$  (use of creatinine clearance per protocol based on chemotherapy regimen)
- Hepatic function, as follows: ( $\leq$  14 days prior to treatment start)
  - Aspartate aminotransferase (AST) ( $\leq 5 \times \text{ULN}$ )
  - Alanine aminotransferase (ALT) ( $\leq 5 \times \text{ULN}$ )
  - Total Bilirubin  $\leq$  1.5 mg/dL
- Magnesium  $\geq$  lower limit of normal ( $\leq$  48 hours prior to treatment start)
- Calcium  $\geq$  lower limit of normal ( $\leq$  48 hours prior to treatment start)
- Prior chemotherapy is acceptable if last dose given  $\geq$  3 weeks prior to registration to this study. [Note: no chemotherapy to be given after resection of liver lesions prior to treatment on this study.]
- Any investigational agent is acceptable if administered  $\geq$  30 days before registration
- KPS  $\geq$  60% (ECOG (or Karnofsky) performance status (*preferably 0 or 1* $\geq$  60% for Karnofsky)
- Histologically confirmed all-RAS wild type . Paraffin-embedded tumor tissue obtained from the primary tumor or metastasis (Prior to

## 6.2 Subject Exclusion Criteria

- Patients  $<$  18 years of age.
- Prior radiation to the liver (Prior radiation therapy to the pelvis is acceptable if completed at least 4 weeks prior to registration.)
- Active infection, ascites, hepatic encephalopathy.
- Prior treatment with HAI FUDR.
- Patients who have had prior anti-EGFR antibody therapy and who have not responded to this treatment will be excluded. However, patients who have responded to prior anti-EGFR therapy are eligible.
- Female patients who are pregnant or lactating – or planning to become pregnant within 6 months after the end of the treatment (female patients of child-bearing potential must have negative pregnancy test  $\leq$  72 hours before registration).

- If a patient has any serious medical problems which may preclude receiving this type of treatment.
- Patients with current evidence of hepatitis A, B, C (ie, active hepatitis)
- Patients with history or known presence of primary CNS tumors, seizures not well-controlled with standard medical therapy, or history of stroke will also be excluded.
- History of allergic reactions attributed to compounds of similar chemical or biologic composition to Panitumumab.
- Serious or non-healing active wound, ulcer, or bone fracture.
- History of interstitial lung disease e.g. pneumonitis or pulmonary fibrosis or evidence of interstitial lung disease on baseline chest CT scan.
- Patients who have a diagnosis of Gilbert's disease.
- History of other malignancy, except:
  1. Malignancy treated with curative intent and with no known active disease present for  $\geq 3$  years prior to registration and felt to be at low risk for recurrence by the treating physician
  2. Adequately treated non-melanomatous skin cancer or lentigo maligna without evidence of disease
  3. Adequately treated cervical carcinoma in situ without evidence of disease

## 7.0 RECRUITMENT PLAN

We will make every effort to include women and minorities. Patients will be recruited from medical and surgical oncology clinics based on their eligibility criteria. The consenting professional will explain in detail the study to the patient and will review the informed consent with the patient. Patients will be made aware of the protocol, its specific aims and objectives, and the potential risks and benefits the patient may incur. Upon signing the requisite three copies of the informed consent, the patient will be registered to Step One of the protocol. This will —pendll the patient to the study, allowing for liver tissue procurement at surgery. If the patient remains eligible for study participation after surgery, he/she will be registered to Step Two, and then will be randomized to Arm A or Arm B. There will be no financial compensation for patients enrolling on this protocol.

## 8.0 PRETREATMENT EVALUATION

Prior to treatment start, patients will undergo the following procedures:

- CT Angiogram or liver triphasic to determine arterial structures: any time prior to surgery
- Perfusion flow scan (TcMAA): any time prior to treatment start
- RAS Testing: any time prior to surgery; if not done previously, adequate tissue will be obtained at surgery
- CT scan of chest, abdomen\*, pelvis: within 6 weeks prior to treatment start
- Surgery, pump placement: within 6 weeks prior to treatment start
- Post-surgery CT chest, abdomen\*, pelvis: within 3 weeks prior to treatment start
- EKG: within 3 weeks prior to treatment start
- MediPort placement: any time prior to treatment start
- HX, PE, BP; Ht / Wt: within 2 weeks prior to treatment start
- Pregnancy test (females of child-bearing potential): 72 hours prior to treatment start
- Magnesium and Calcium: within 48 hours prior to treatment start
- KPS, CBC with diff/plts, albumin, LDH, BUN, creatinine, alk phos, SGOT, SGPT, bilirubin, CEA, serum electrolytes: within 14 days prior to treatment start.

\* *MRI may be obtained instead of CT if patient's disease is not visible on CT*

8.1 Patients will have full resection of liver metastases along with pump placement within 6 weeks prior to treatment. Surgeons will report whether the resection is R0 or R1 and whether patients have positive or negative lymph nodes.

## 9.0 TREATMENT/INTERVENTION PLAN

9.1 Chemotherapy will be administered on a 5-week cycle basis. Pump therapy with FUDR and Dex will be administered on Day 1 of each cycle. The pump will be emptied and filled with heparin and normal saline on Days 15 and 29. Systemic chemotherapy will be administered on Days 15 and Day 29 of each cycle. Treatment recycles on Day 36.

On Days 15 and 29, patients will receive systemic chemotherapy. Patients on the panitumumab arm will receive the drug over a 60 minute infusion first. CPT-11/LV will be administered subsequently via a Y-line over a 30 to 60 minute infusion, and 5FU will follow by a 48-hour infusion.

9.2 For the first cycle, the dose of FUDR will be calculated based on the predetermined flow rate provided by the pump manufacturer. Thereafter, doses will be adjusted (lowered, if necessary, but never increased) based on actual observed flow rate. The pump will be filled with FUDR, Dexamethasone, heparin and saline.

Dose calculation:

FUDR:  $\frac{0.12 \text{ mg/kg} \times \text{kg (patient weight)} \times \text{pump volume}}{\text{pump flow rate}}$

Dexamethasone: flat dose of 25 mg

*Overweight patients:*

If a patient is 35% above ideal weight, dose of FUDR chemotherapy will be calculated as follows:

To calculate Ideal Body weight (kg):

Males:  $50\text{kg} + (2.3 \times \text{height in inches above 5 ft})$   
(i.e.: for a patient who is 5'10", use 10)

Females:  $45.5\text{ kg} + (2.3 \times \text{height in inches above 5 ft})$

*Example:* An overweight male is 106 kg and 5'11"

$50\text{kg} + (2.3 \times 11) = 50\text{kg} + 25.3 = 75.3$  is the Ideal Body Weight

To calculate Ideal Average weight (kg):

Actual weight + Ideal Body Weight

2

*Using the male example from above:*

$106 + 75.3 = 181.3 \div 2 = 90.65$  is the Ideal Average Weight

Use the Ideal Average Weight to calculate the FUDR dose in patients who are overweight\*.

\* If PI feels the patient is an appropriate weight, the ideal average weight equation should not be used and patients can have the regular dose calculation of FUDR.

Heparin: 30,000 units total dose

Normal saline: quantity sufficient to make total reservoir volume of 30 ml.

If no dose modification due to toxicity is required, the dosages given above (adjusted for changes in weight and pump flow rate) will be repeated on Day 1 of Cycle 2 and all subsequent cycles.

Pump Flow Rate: The first total dose of FUDR should be calculated using the precalculated flow rate provided by the pump manufacturer. The pump will be filled with FUDR, Dexamethasone, heparin and saline. Thereafter, the flow rate should be recalculated each cycle. If a significant ( $\geq 20\%$ ) discrepancy is seen, notify the Principal Investigator.

To recalculate flow rate, the amount of any residual infusate removed from the pump at the end of the 14-day infusion is subtracted from the total pump volume. This result is divided by the number of days in the infusion period (usually 14). See example below:

*Example:* Pump is filled with 30.0 ml infusate on Day 1. At pump emptying on Day 15, pump yields 12 ml residual.

Total infusion over the 14-day period was  $30 - 12 = 18$  ml

Flow rate =  $18 \text{ ml} \div 14 \text{ days} = 1.3 \text{ ml/day}$

- 9.3 On Days 15 and 29 of each cycle, the pump will be emptied and then filled with 30,000 units of heparin in normal saline (q.s. 30cc) for 14 days.
- 9.4 Patients must meet all hematologic and blood chemistry criteria outlined in Section 6.0 before beginning the first cycle of therapy. For subsequent cycles, patients must meet the following criteria:

WBC	$\geq 2.5 \text{ K/uL}$
ANC	$\geq 1.0 \text{ K/uL}$
Platelet count	$\geq 75 \text{ K/uL}$
Creatinine	$\leq 1.8 \text{ mg/dL}$
Bilirubin	$< 1.5 \text{ mg/dL}$

If counts are outside these levels on date of schedule treatment, therapy will be delayed one to two weeks or at the discretion of the treating physician.

Parameters for treatment with FUDR via intrahepatic pump are outlined in Section 11.4.2.

- 9.5 The starting panitumumab dose is 6 mg/kg. The total dose may be rounded up or down by no greater than 10 mg. The panitumumab dose will be calculated based on the subject's actual body weight at baseline and will not be re-calculated unless the actual body weight changes by at least 10%.

9.6 All reasonable efforts will be made to adhere to treatment and evaluation schedules, however minor infrequent variations to accommodate holidays, transportation issues, or patient's personal schedule will be permitted if these do not, in the opinion of the investigator, constitute a major safety or compliance issue. Such variations, assuming they do not occur with unreasonable frequency or regularity, will not be considered protocol violations.

## 10.0 EVALUATION DURING TREATMENT/INTERVENTION

	Day 1* each cycle	Days of systemic chemotherapy**	Q10 weeks approximately after treatment start
HX, PE, MD or NP visit	X		
HX, Nurse visit		X	
Tox assessment	X		
Weight	X		
KPS	X		
CBC, Plts	X	X	
BUN, Creat	X	X	
Bili, SGOT, SGPT	X	X	
Alk phos, LDH	X	X	
Electrolytes	X	X	
CEA	X	X	
Magnesium (for patients randomized to Panitumumab arm)	X	X	
Calcium	X	X	
CT Chest/abdomen/pelvis***			X

\* Or within 48 hours prior to Day 1

\* Or within 72 hours prior to Day 15 and Day 29

\*\*\* MRI may be obtained instead of CT if patient's disease is not visible on CT. Allowances of +/-3 weeks will be acceptable.

10.1 While being treated with protocol therapy, patients will be seen at or prior to the first day of each cycle by their medical oncologist.

In cases approved by the Principal Investigator, patients randomized to Arm B (no panitumumab) can see local oncologists for systemic treatments.

10.2 Patients will be assessed for adverse events prior to administration of systemic chemotherapy, panitumumab, or HAI.

10.3 Patients will have an end of study assessment for toxicity.

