#### **14.0 BIOSTATISTICS**

This study will 1:1 randomize 78 patients to two treatment arms: HAI FUDR and dexamethasone with systemic chemotherapy, +/- systemic Panitumumab. Randomization procedures will be discussed in section 15.2.

The primary endpoint is 15 month recurrence free survival (RFS). Based on an exact binomial single stage design, with 39 patients in each arm we are able to differentiate between unacceptable 15 month RFS of 50% and acceptable 15 month RFS of 70% with type I error (falsely accepting a non-promising therapy) and II error (falsely rejecting a promising therapy) rates of 10 % each. For a particular arm, if 24 or more patients are alive and disease free at 15 months the regimen in that arm will be considered worthy of further investigation. We will use the —pick the winner— format based on the randomized phase II clinical trials approach proposed by Simon et al. (1985) to differentiate between 15 month RFS of 50% and 70%. The pick the winner role only occurs if both regimens are efficacious. If the number of patients who are disease free and alive at 15 months in one arm is at least 24 and it exceeds by at least 3 patients the number of alive and disease free patients at 15 months in the other arm, then the arm with the higher 15 months RFS would be declared the winner. If neither arm had at least 24 patients alive and disease free at 15 months, the regimens in both arms would be considered unworthy of further evaluation. The probability of selecting the better regimen is 85%; the probability that no regimen is selected is approximately 9%, while the probability of a tie is 6 % (Simon R, Wittes RE, Ellenberg SS. (1985). Randomized phase II clinical trials. *Cancer Treat Rep* 69, 1375-1381.)

RFS will also be estimated using the Kaplan Meier method. As secondary endpoint, overall survival will be estimated by the Kaplan Meier method. Associations between biomarkers and RFS and overall survival will be assessed using the log-rank test. In each arm, safety and tolerability will be summarized using descriptive statistics.

The prevalence of RAS mutations is about 40%; therefore we would have to approach about 120 patients in order to accrue 78 patients. On average, we see about 40 eligible patients per year; therefore we would need three years to reach 120.

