### **17.2.2 Reporting Procedures for All Adverse Events to Amgen**

All AEs occurring after informed consent signing observed by the investigator or reported by the subject (whether or not attributed to investigational product) will be reported. The investigator is responsible for ensuring that all adverse events observed by the investigator or reported by subjects are properly captured in the subjects' medical records.

An adverse event is defined in the International Conference on Harmonization (ICH) Guideline for Good Clinical Practice as —any untoward medical occurrence in a patient or clinical investigation subject administered a pharmaceutical product and that does not necessarily have a causal relationship with this treatment. (ICH E6:1.2). The ongoing review of safety data will include review of clinical AEs and SAEs including skin-related toxicity assessment and laboratory studies. The CTCAE version 4.0 will be used to grade all AEs, except Panitumumab related toxicity which will be graded by modified CTCAE version 3.0 Dermatology Skin Assessment (Appendix B). The investigator is responsible for reviewing laboratory test results and determining whether an abnormal value in an individual study subject represents a change from values before the study. In general, abnormal laboratory or clinical findings without clinical significance (Grades 1 and 2 or based on the investigator's judgment) should not be recorded as adverse events; however, laboratory value changes requiring therapy or adjustment in prior therapy are considered adverse events. All Grade 3 and Grade 4 or clinically significant toxicities will be recorded.

The following adverse event attributes must be assigned by the investigator:

- Adverse event diagnosis or syndrome(s) (if known, signs or symptoms if not known)
- Event description (with detail appropriate to the event)
- Dates of onset and resolution
- Severity
- Assessment of relatedness to study treatment
- Action taken.

Amgen may request follow-up information.

Medically significant adverse events considered related to the investigational product by the investigator or the sponsor will be followed until resolved or considered stable.

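### On-treatment magnesium is scheduled only in Arm A and local systemic treatment is allowed only in Arm B, so on-treatment toxicity is not ascertained alike in the two arms

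*Combined protocol and SAP*

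**What the plan says.** Section 2.0 makes toxicity the first secondary objective. Section 14.0 plans the analysis within each arm: "safety and tolerability will be summarized using descriptive statistics". It plans no between-arm safety test.

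Two provisions in Section 10.0 differ by arm:

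- **Magnesium.** The table row reads "Magnesium (for patients randomized to Panitumumab arm" and is ticked for Day 1 and for days of systemic chemotherapy. The other scheduled blood tests, including calcium and electrolytes, carry no arm restriction.
- **Place of treatment.** Section 10.1: "In cases approved by the Principal Investigator", "patients randomized to Arm B (no panitumumab) can see local oncologists for systemic treatments". Arm A has no matching provision. Section 5.6.1 gives a reason: study panitumumab may be given only under the direction of the trial's investigators.

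Other provisions are the same in both arms:

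- Section 8.0 requires "Magnesium and Calcium: within 48 hours prior to treatment start", and Section 6.1 makes a normal-range lower bound for magnesium an entry criterion.
- Section 10.1 states that "patients will be seen at or prior to the first day of each cycle by their medical oncologist". The table ticks the toxicity assessment on Day 1 only.
- Section 10.2: "Patients will be assessed for adverse events prior to administration of systemic chemotherapy, panitumumab, or HAI". Section 10.3 adds an end-of-study toxicity assessment.
- Section 17.2.2: "All Grade 3 and Grade 4 or clinically significant toxicities will be recorded".

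**The concern.** A side-by-side toxicity table is read as if both columns had been looked at equally hard. Here they may not be. A laboratory abnormality that is looked for in one arm and not in the other will appear as a treatment difference whatever the truth. For systemic-treatment days, an adverse event or low blood count seen in a local office reaches the trial record only if someone sends or retrieves it, and the documents describe no procedure for that. Both asymmetries act in the same direction: they can only lower what is recorded in Arm B.

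The stake is the informal safety comparison. Section 3.2.3 itself raises additive gastrointestinal toxicity when panitumumab is combined with chemotherapy that is already toxic to the gut. Readers will therefore compare the two columns even though no test is planned.

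**Working it through.** **The plan's own figure.** The documents give no figure for a safety comparison. The 39 patients per arm come from the efficacy design in Section 14.0, which reproduces: with a cut-off of 24 of 39, the exact type I error is 0.0998 at a 15-month RFS of 50% and the power is 0.906 at 70%. That rule counts patients alive and disease free and uses no toxicity data, so nothing below affects it.

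**Step 1: magnesium.**

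| | Baseline | Day 1 of each cycle | Systemic-chemotherapy days |
|---|---|---|---|
| Arm A | scheduled | scheduled | scheduled |
| Arm B | scheduled | not scheduled | not scheduled |

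The baseline value cannot stand in for the missing ones, because Section 11.2 says hypomagnesaemia appeared six weeks or more after panitumumab was started. An asymptomatic fall in Arm B would be found only by an unscheduled test. The Arm B rate would then reflect who happened to be tested, so the difference between arms is not interpretable. The number of severe cases is small: at the 2% grade 3 or 4 rate cited in Section 11.2, 39 × 0.02 = 0.78 patients are expected in Arm A. The documents cite no rate for lower grades.

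**Step 2: other toxicity on Days 15 and 29.** Let p be the true rate of an event, equal in both arms; f the share of Arm B events that arise under local care; and s the probability that such an event reaches the trial record. Arm A is assumed to be fully captured. Then:

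- recorded Arm B rate = p × (1 − f × (1 − s))
- false excess in Arm A = p × f × (1 − s)

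The documents give none of p, f and s. The values below are assumptions chosen to show a range.

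| p | f | s | False excess (points) | Patients out of 39 |
|---|---|---|---|---|
| 25% | 10% | 0.9 | 0.25 × 0.10 × 0.10 = 0.25 | 0.1 |
| 25% | 50% | 0.5 | 0.25 × 0.50 × 0.50 = 6.25 | 2.4 |
| 40% | 10% | 0.9 | 0.40 × 0.10 × 0.10 = 0.4 | 0.2 |
| 40% | 50% | 0.5 | 0.40 × 0.50 × 0.50 = 10 | 3.9 |

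At s = 1 the excess is zero for any p and f. For comparison, the standard error of a difference between two arms of 39 is √(2p(1 − p)/39), which is 9.8 points at p = 25% and 11.1 points at p = 40%. One patient is 1/39 = 2.6 points.

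**Step 3: the table against Section 10.2.** The table places the toxicity assessment on Day 1 only, while Section 10.2 asks for an adverse-event assessment before each systemic dose, which includes Days 15 and 29. The mismatch applies to both arms and is not in itself a source of difference. It does leave open what must be collected on the days when an Arm B patient may be treated elsewhere.

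**The case against.** The strongest reply is that most of the safety data are collected alike. Every patient is seen at or before Day 1 of each cycle, and the next Day 1 (Day 36) comes 7 days after Day 29, so symptoms from the interval can be asked about. Section 10.2 applies wherever a dose is given. Sections 17.2 and 17.2.2 require serious and grade 3 or 4 events to be reported or recorded regardless of arm. Section 16.0 assigns data collection and abstraction to a research assistant, and Section 16.1 adds missing-data reports and audits at least twice a year. Local treatment needs approval case by case, and restricting it to Arm B follows from the handling rule for study panitumumab. Magnesium is monitored where the known risk lies.

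Most of this stands. It explains the asymmetries and limits the second one. It does not supply an on-treatment magnesium value in Arm B. Nor does a Day 1 history recover a low neutrophil or platelet count on a local Day 29 sample unless the laboratory report is obtained.

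Two stronger readings are tempting, and the documents support neither:

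- A reader might infer that the safety comparison is biased against panitumumab. Beyond magnesium this is a possibility only. If local records are complete, the place of treatment creates no bias.
- A reader might infer that a locally treated Arm B patient has every Day 15 and Day 29 contact away from the centre. Sections 9.1 and 9.3 also place pump emptying and refilling on those days, and Section 10.1 moves only systemic treatments. The documents do not say how many contacts are off site.

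**Conclusion.** The point holds for on-treatment hypomagnesaemia. With no scheduled measurement in Arm B, its rate should not be set against that of Arm A. At the cited severe rate this concerns about 0.8 expected Arm A patients.

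For other toxicity on Days 15 and 29, understatement in Arm B is a plausible risk of unknown size. The illustrative range of 0.25 to 10 points rests on assumed event rates, shares under local care and capture probabilities, together with an equal true rate and full capture in Arm A. Even its upper end is no larger than about one standard error of the difference.

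The primary endpoint and the selection rule are untouched, and no formal safety test is affected. This is a minor issue of collection and reporting, worth settling because the remedy is cheap and local records may be hard to recover later.

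**What to change.** 1. **Magnesium.** Either state in Section 14.0 that on-treatment hypomagnesaemia is reported for Arm A only, with no between-arm comparison, or add magnesium to the chemistry already drawn in Arm B on the Arm A schedule. The first option costs one sentence. The second costs one extra assay per draw, which Section 17.1.1 suggests would be billed to the patient unless that is changed.
2. **Tables.** Show side-by-side toxicity rates from the Day 1 assessments common to both arms, next to the all-source table, and label the source of each. The cost is one more table. The Day 1 table will omit abnormalities seen only on Day 15 or 29 blood tests in either arm, which is why both tables are needed.
3. **Local visits.** Name who obtains the adverse-event and laboratory records from each local Day 15 and Day 29 visit, on the same form used at the centre, and report how many Arm B patients and visits were local. The cost is a form and some chasing by the research assistant.
4. **Consistency.** Reconcile the Day 1-only toxicity-assessment tick in the Section 10.0 table with Section 10.2, for both arms. The cost is an editorial change.
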